Date: 25/01/2022

Official Title: The Effect of Different Neuromodulation Techniques

in the Treatment of Multiple Sclerosis Patients With Neurogenic

Bladder Dysfunction

Study Protocol

Inclusion criteria for the study;

- 18-65 years old
- Woman
- Volunteer to participate in the study
- Neurogenic overactive bladder due to MS
- EDSS < 7.0
- Not benefiting from pharmacological treatment

Exclusion criteria from the study;

- With urinary tract infection
- Diagnosed with diabetes mellitus
- Using diuretic medication
- Using clean intermittent catheterization
- Having a history of different urological diseases
- Those who have conditions that would be contraindicated for electrical stimulation (pacemaker, brain pacemaker, prosthesis)

Evaluation methods;

- Demographic information form
- Extended disability status scale (EDSS)
- Overactive bladder questionnaire (OAB-V8)
- Incontinence severity index (ISI)
- Incontinence quality of life scale (I-QOL)
- Voiding diary
- Urodynamics

According to the treatment protocols of the patients to be included in the study; will be divided into 2 groups as transcutaneous posterior tibial nerve stimulation group (8 patients) and repetitive transcranial magnetic stimulation group (8 patients). Which method will be applied to which individual will be determined randomly. Treatment sessions will be carried out for 5 consecutive days in 2 consecutive weeks, 1 time per day for a total of 10 sessions. The urological parameters of the patients in all groups will be evaluated before and after the treatment.

Transcutaneous Posterior Tibial Nerve Stimulation Group

The treatment will be carried out by the physiotherapist using the Tenstem Eco Basic device. The treatment parameters will be applied with a pulse current time of $200~\mu sec$, a fixed frequency of 10~Hz, a treatment time of 20~minutes, and a current intensity that the patient can tolerate, which will not cause flexion in the big toe or fan movement in the other fingers. Self-adhesive surface electrodes will be used for stimulation. During the treatment, the patient will lie on his back. The negative electrode will be placed 2 cm posterior to the medial malleolus and the positive electrode will be placed 10~m proximal.

Repetitive Transcranial Magnetic Stimulation Group

The treatment will be applied with a Power Mag device. The treatment will be internally cooled 70 mm double coil and 110 mm round coil, accompanied by a physiotherapist and neurologist. The coil will be placed on the precentral gyrus. Practices will be held, with each session lasting 20 minutes. Cortical excitability will be provided by high frequency (HF) stimulation (5-Hz).

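### The only treatment-related exclusion is worded for electrical stimulation and does not name seizure history, although any woman enrolled may be allocated to 5 Hz magnetic stimulation over the precentral gyrus

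*Protocol*

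**What the plan says.** The protocol lists six inclusion and six exclusion criteria. Five of the exclusions deal with urinary infection, diabetes, diuretics, intermittent catheterisation and other urological disease. The sixth is the only one that concerns a study treatment: "Those who have conditions that would be contraindicated for electrical stimulation (pacemaker, brain pacemaker, prosthesis".

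Sixteen women are to be split into two groups of 8, one receiving transcutaneous tibial nerve stimulation and the other repetitive transcranial magnetic stimulation (rTMS). On assignment the protocol says: "Which method will be applied to which individual will be determined randomly". Each group has 10 sessions over two weeks.

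The section on the rTMS group gives the site, "The coil will be placed on the precentral gyrus", and the intended action, "Cortical excitability will be provided by high frequency (HF) stimulation (5-Hz". It also says that sessions are "accompanied by a physiotherapist and neurologist".

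The SAP text deals with descriptive statistics and tests. It does not bear on eligibility.

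**The concern.** Under random allocation a patient must be fit for either treatment before she is assigned. The two treatments here differ in kind: one passes current through skin electrodes at the ankle, and the other applies a magnetic coil over the motor cortex. An exclusion written for the first need not cover the risks of the second.

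The risk in question is seizure. That repeated stimulation of the motor cortex can provoke a seizure in a susceptible person is general clinical knowledge, taken here as an assumption; neither document states it. The protocol does say that the treatment is meant to act on cortical excitability, which is why the question arises for this trial in particular. What is at stake is a preventable harm to a participant. A lesser consequence is that a woman found unsuitable only after allocation would be lost from the rTMS group, while a similar woman in the tibial group would stay.

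**Working it through.** There is no figure in the plan to reproduce. The check is a reading of the criteria against the rTMS description.

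**Step 1. Does any criterion cover seizure or magnetic stimulation?**

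| Criterion | Tied to a study treatment? | Names seizure, epilepsy or magnetic stimulation? |
|---|---|---|
| Six inclusion criteria (age, sex, consent, bladder diagnosis, EDSS limit, drug failure) | No | No |
| "With urinary tract infection" | No | No |
| "Diagnosed with diabetes mellitus" | No | No |
| Diuretics | No | No |
| Intermittent catheterisation | No | No |
| Other urological disease | No | No |
| Contraindication to electrical stimulation | Yes | No |

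Count: 1 of 12 criteria concerns a study treatment, and 0 of 12 name seizure, epilepsy or magnetic stimulation. The rTMS section adds no screening condition.

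**Step 2. What does the one relevant criterion cover?** Two of the named items, the cardiac and the brain pacemaker, matter for magnetic stimulation as well. Other metal in the head is covered only if the screener counts it as a prosthesis. Seizure history is covered only if the screener reads the bracket as a list of examples and also regards that history as a contraindication to electrical stimulation.

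**Step 3. Who can reach the coil?** With 8 of 16 places in the rTMS group, an eligible woman's chance of assignment to it is 8/16 = 50%, taking allocation as 1:1, as the equal group sizes imply. Nothing in the protocol makes that chance depend on neurological history.

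**Step 4. What stands in the way?**
- *Before allocation.* The criterion "Neurogenic overactive bladder due to MS" and the EDSS limit imply a neurological assessment at entry. A seizure history may well come to light there, but no stated criterion makes it a reason to exclude.
- *After allocation.* A neurologist is present at rTMS sessions and could decline to treat. No stated rule directs this, and by then the woman already belongs to the rTMS group.

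**Step 5. Can the risk be given a number?** No. The chance that at least one such woman is among the 8 is 1 − (1 − p)^8, where p is the proportion of otherwise eligible women with a seizure history. The documents give no value of p, so any result would only restate the value assumed.

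**The case against.** The strongest reply is that the criterion's opening words are general. It excludes contraindicating conditions, and the three items in the bracket can be read as examples. On that reading a screener is free to exclude a woman with a seizure history. The list also includes a brain pacemaker, which matters more directly for a coil over the head than for electrodes at the ankle. That suggests electrical stimulation may have been a loose term for both methods. This much stands: a reader might infer that the protocol deliberately admits women with a seizure history, or that the rTMS group is not screened at all, and the text supports neither. It supports only that the history is not named and that its exclusion rests on the screener's interpretation.

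It is also fair to say that the documents do not call seizure history a contraindication to rTMS. The protocol gives no intensity, pulse count or train pattern, so the seizure risk of this regimen cannot be judged from it. Consent pages are not in the public text and could contain device-specific questions. These points limit certainty about practice. They do not alter the eligibility list, which reads as complete.

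A second tempting inference is that the gap biases the comparison through selective loss from the rTMS group. That would need the women lost to respond differently from the rest, and nothing in the documents suggests so. Loss unrelated to response causes no bias. For any one woman, moreover, the two harms exclude each other: if the neurologist stops before treating her she is lost but not exposed, and if not she is exposed but not lost.

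**Conclusion.** The point holds as a gap in the wording of one safety criterion. Applied as written, the criteria can admit a woman with a seizure history and give her an even chance of 10 sessions of 5 Hz stimulation over the precentral gyrus. Only a screener's discretion, or a neurologist's intervention after allocation, would prevent it. The conclusion rests on two assumptions: that cortical rTMS can provoke seizures in susceptible people, and that no unwritten screening already deals with this. If such screening exists, writing it down costs almost nothing.

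The frequency of the problem cannot be estimated from the documents, and its effect on the treatment comparison is negligible. It is a cheap improvement on patient-safety grounds and does not put the trial's inference in doubt. Confidence is medium, because practice at the site may already be better than the text.

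**What to change.** Reword the sixth exclusion along these lines: *conditions contraindicated for electrical or transcranial magnetic stimulation (pacemaker, brain pacemaker, prosthesis, metal or electronic implant in the head, history of seizure or epilepsy)*. Apply it to every woman before allocation, at the assessment that establishes the MS diagnosis and EDSS, so that both groups are drawn from women fit for either treatment.

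The cost is one reworded criterion and one extra screening question. Some women may have to be replaced at screening; how many depends on a prevalence that the documents do not give. The downside is that the results would not apply to women with a seizure history, including those who could safely have had tibial nerve stimulation.

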## **Statistical Analysis Plan**

Statistical analysis of the data obtained from the study will be done in the SPSS 22.0 package program. The mean standard deviation, median, minimum and maximum values will be used to define the data. Comparison of continuous variables between groups will be done with Mann Whitney U test, comparison of discrete variables will be done with chi-square test. Spearman or Pearson correlation test will be used to evaluate the correlation between variables. In the data analysis, p < 0.05 level will be considered statistically significant.

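### The only planned between-group test for continuous outcomes gives the baseline no stated role; ANCOVA on ranks would use it at little cost

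*SAP*

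**What the plan says.** Below its list of evaluation methods, the protocol sets two arms of 8 patients and states: "Which method will be applied to which individual will be determined randomly". On timing it states: "The urological parameters of the patients in all groups will be evaluated before and after the treatment". It describes no stratification by baseline severity.

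The section headed Statistical Analysis Plan gives one rule for continuous variables, "Comparison of continuous variables between groups will be done with Mann Whitney U test", and one for the rest: "comparison of discrete variables will be done with chi-square test". It adds descriptive statistics, a Spearman or Pearson correlation and a 0.05 significance level. It names no ANCOVA, mixed model, paired test or other use of the baseline in comparing the arms. It does not say whether the tested variable is the post-treatment value or the change.

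**The concern.** A baseline value of the same outcome is often the best available predictor of the post-treatment value. With 8 per arm, leaving that information out can cost noticeable power. The rule as written can be read in two ways. Testing post values ignores the baseline. Testing changes subtracts all of it, which adds noise when baseline and post values correlate weakly. Which version does better depends on a correlation that the documents do not give.

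The secondary matter is that the SAP leaves the choice between the two versions open. If both were run and the favourable one reported, the error rate would exceed the stated 5%.

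**Working it through.** **Inputs from the documents.** 8 v 8, random assignment, two measurement times, Mann-Whitney test, 0.05 level. No power, effect size or SD is stated, so there is no planned figure to reproduce.

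**Assumptions.** Two-sided test; equal SD at both times; no dropout; rho from 0 to 0.8; effect 0.5 or 1 SD; normal or lognormal data (log-SD 1, effect on the log scale).

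**Step 1: the planned test.** There are C(16,8) = 12,870 allocations. The exact test rejects at U ≤ 13, with two-sided size 0.0499. Over all randomisations, either version holds 5%.

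**Step 2: residual SD, in outcome SD units.** Post value: 1. Change: √(2(1−rho)). Linear ANCOVA: √(1−rho²).

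| rho | post | change | ANCOVA |
|---|---|---|---|
| 0.3 | 1 | 1.183 | 0.954 |
| 0.5 | 1 | 1.000 | 0.866 |
| 0.7 | 1 | 0.775 | 0.714 |
| 0.8 | 1 | 0.632 | 0.600 |

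Change is noisier than post when rho is below 0.5 and less noisy above it.

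**Step 3: chance baseline imbalance.** The SD of the baseline difference is √(2/8) = 0.5 SD. A gap above 0.5 SD therefore occurs with probability 2(1−Φ(1)) = 0.317 per outcome. When it does, in one direction, the mean gap is 0.5·φ(1)/(1−Φ(1)) = 0.763 SD. Post values then shift by 0.763·rho (0.38 SD at rho 0.5) and changes by −0.763·(1−rho) (−0.38 SD), that is, in opposite directions.

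**Step 4: simulated power.** 40,000 trials per scenario. Rank ANCOVA regresses the rank of the post value on group and the rank of the baseline (t test, 16−3 = 13 df).

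| Scenario, rho 0.3/0.5/0.7/0.8 | Rank ANCOVA | Mann-Whitney, post | Mann-Whitney, change |
|---|---|---|---|
| 1 SD, normal | 45/51/63/75% | 44/44/44/45% | 34/44/64/82% |
| 1 SD, lognormal, effect a reduction | 45/51/63/75% | 44/44/44/45% | 21/26/38/49% |
| 0.5 SD, normal | 15/17/22/27% | 15/15/15/15% | 12/15/22/30% |

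In the lognormal row, rank ANCOVA and the post test are unchanged because taking exponentials preserves ranks. Only the change score moves, and it depends on direction: with an increase instead of a reduction it has 37/46/64/78%.

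The null rate of rank ANCOVA is 4.9 to 5.4%. With assumed 5-level scores, which produce ties, it is 4.9 to 5.6%.

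**Step 5: the unnamed variable.** With no true effect, at least one of post and change is significant in 9.0/9.2/9.4% of trials (rho 0.3/0.5/0.7, normal). Adding percent change gives 10.5 to 11.3% (lognormal). With normal data the two versions differ on significance in 32/35/42% of trials at 1 SD, 17/20/25% at 0.5 SD and 8 to 9% at no effect.

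**The case against.** The best defence is that a rank test is a sensible choice for scores and small groups, and that declining to adjust is an efficiency choice. That stands as far as validity goes. Three stronger readings are tempting, and the documents support none of them.

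- **That the planned test is invalid or biased by imbalance.** The 32% chance of a baseline gap above 0.5 SD is already part of the 5% error rate of a randomised comparison. Imbalance costs precision; it does not invalidate a test fixed in advance.
- **That the unnamed variable is the main defect and the error rate is 9%.** The SAP omits a detail. Nothing in it says that both versions will be run and the better one kept. The 9% applies only if that happens, and it is not an upper bound because other forms of change could be tried. Nor is the disagreement between versions an error rate: part of it is low power.
- **That adjustment always wins.** With normal data, rank ANCOVA is clearly ahead of the better Mann-Whitney version only around rho 0.5. At rho 0.3 and 0.7 it is within about a point, and at rho 0.8 it is 6 to 7 points behind change.

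What survives is that the better version cannot be chosen without knowing rho, the shape of the data and, for skewed data, the direction of effect. Rank ANCOVA comes close to the better version or beats it without that knowledge, and remains rank-based.

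**Conclusion.** The point holds as a cheap improvement. The baseline is collected but has no stated role in the treatment comparison. With a 1 SD effect and normal data, rank ANCOVA gains 45 − 34 = 11 points over change at rho 0.3, 51 − 44 = 7 over either version at rho 0.5, and 63 − 44 = 19 over post at rho 0.7. At 0.5 SD the gains over post are 0, 2 and 7 points at those values, and power stays at 30% or below whichever of the three tests is used.

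The omission can be read directly from the SAP. Its size rests on the assumed rho, effect and distribution; a 1 SD difference between two active stimulation methods has no support in the documents. One part of the SAP file, outside the section quoted here, was not available; if it specifies a baseline-adjusted analysis, the point falls.

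**What to change.** Keep chi-square for discrete variables and Mann-Whitney for continuous variables measured once. For every continuous or score outcome measured at both times, replace Mann-Whitney with:

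> The between-group comparison will be ANCOVA on ranks: the rank of the post-treatment value on group and the rank of the baseline value of the same outcome, two-sided 5%. The median change in each group will be reported as description only.

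Use this one scale for all such outcomes, so that neither the tested variable nor the scale is left to choose once data are seen. A permutation p-value is optional. No second test on changes is needed; it would bring back conflicting results.

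The work is a change of SAP wording, with no new data. The SAP names a single program ("Statistical analysis of the data obtained from the study will be done in the SPSS 22.0 package program"). The null rates above come from ordinary ANCOVA on ranks, so no permutation script is required.

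Costs in power:
- about 2 points against Mann-Whitney on post if rho is near 0;
- 6 to 7 points against Mann-Whitney on change at rho 0.8 with normal data;
- up to about 7 points against untransformed ANCOVA with normal data at rho up to 0.7, and about 9 at rho 0.8.

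A rank-scale effect is also harder to interpret clinically, which is why the median changes are reported beside it. The change does not cure the small sample.

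### Five bladder outcomes share one p < 0.05 rule and none is primary: if any one result counts, about 11–23% of trials show a false group difference, not 5%

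*SAP*

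**What the plan says.** The evaluation methods in the Protocol form one unranked list of seven items. Two of them, the demographic form and EDSS, describe the patients. The other five are bladder outcomes: OAB-V8, ISI, I-QOL, the voiding diary and urodynamics. The only other statement about outcomes is "The urological parameters of the patients in all groups will be evaluated before and after the treatment". It singles out no parameter and does not say whether the groups will be compared on after-treatment values or on changes.

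The SAP gives the tests: "Comparison of continuous variables between groups will be done with Mann Whitney U test, comparison of discrete variables will be done with chi-square test". It adds Spearman or Pearson correlations between variables, and closes with one threshold for all of this: "In the data analysis, p < 0.05 level will be considered statistically significant".

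The documents as supplied contain no primary outcome, testing order, multiplicity adjustment or exploratory label.

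**The concern.** With five outcomes of equal standing and one threshold for each, the plan does not tell a reader which result decides the comparison of tibial nerve stimulation with magnetic stimulation. A report could rest on whichever instrument happened to reach p < 0.05.

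If the techniques differ on none of the outcomes, the chance that at least one of five tests falls below 0.05 is well above 5%. An isolated significant result would then be weak evidence that one technique is better, and a reader could not tell from the plan whether that outcome had been chosen in advance.

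**Working it through.** The documents state no power, sample-size or familywise error figure, so there is none of the plan's own to reproduce. The only stated error rate is the per-test level.

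**Inputs from the documents.** Per-test level 0.05 and the Mann-Whitney U test for continuous variables (SAP, Statistical Analysis Plan); 8 patients in each of two randomised groups, and five bladder outcome instruments (Protocol).

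**Assumptions.** Two-sided tests, since the SAP does not state sidedness; one continuous, untied variable per instrument; the same correlation between every pair of outcomes, varied from 0 to 0.9; no true difference on any outcome; any one p < 0.05 counts as a finding.

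**Step 1: size of one test.** There are C(16,8) = 12,870 equally likely rank allocations. With U the smaller of the two statistics:

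- U ≤ 13: 642/12,870 = 0.04988, so p < 0.05.
- U = 14: 836/12,870 = 0.06496, so not significant.

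The normal approximation without continuity correction gives 0.0460 at U = 13 and 0.0587 at U = 14. The cut-off is therefore the same whichever p-value is used.

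**Step 2: five independent tests.** 1 − (1 − 0.05)^5 = 0.2262. With the attained size, 1 − (1 − 0.04988)^5 = 0.2257.

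**Step 3: correlated outcomes.** Equicorrelated normal outcomes were simulated in 8 v 8 trials (200,000 per correlation), rejecting at U ≤ 13. The large-sample column is a cross-check that uses normal tests and numerical integration. The last column assumes that the diary and urodynamics supply three variables each: 3 + 3 + 3 = 9 tests.

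| Correlation (assumed) | Five tests, Mann-Whitney | Five tests, large-sample normal | Nine tests, Mann-Whitney |
|---|---|---|---|
| 0 | 22.6% | 22.6% | 36.7% |
| 0.5 | 19.2% | 18.3% | 28.5% |
| 0.7 | 15.9% | 14.8% | 22.3% |
| 0.8 | 13.8% | 12.7% | 18.6% |
| 0.9 | 11.3% | 10.2% | 14.2% |

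**Step 4: tied scores.** Questionnaire scores will have ties. Five tests on scores with 5 levels (tie-corrected normal approximation, 20,000 runs) give 21.8%, 18.5%, 15.6% and 11.4% at correlations 0, 0.5, 0.7 and 0.9. With 9 levels the rates are 22.5%, 18.6%, 15.6% and 11.1%. Ties barely change the answer.

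**Step 5: one named primary outcome.** The exact rate is 4.99% (Step 1). In simulation it is 4.9–5.1% at every correlation.

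Outcomes that would go to the chi-square test were not modelled.

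**The case against.** The strongest reply is that the error depends on a rule the plan does not contain. The documents state no hypothesis, success criterion or superiority claim. The threshold sentence can be read as an ordinary per-comparison level for a small study, and at that level each untied Mann-Whitney test has its proper size of 4.99%. This is right as far as it goes: the 11–23% holds only if any one result is allowed to count. But neither document calls the study a pilot or its comparisons exploratory, and the SAP sets a significance threshold without saying which test it is meant to decide.

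A second reply is that five is a count of instruments, not of tests. The diary and urodynamics may each supply several variables, and ISI may be treated as discrete. That stands as a limit on precision. More variables raise the rate, as the nine-test column shows; the effect of the chi-square route is not quantified.

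Third, the two ends of the range are set by assumption, and neither complete independence nor a uniform 0.9 is argued to be realistic for overlapping bladder measures. This also stands. Even at 0.9, however, the rate is more than twice 5%.

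Finally, naming a primary outcome is not the only remedy. Bonferroni over five tests also controls the error: at 0.01 each, the exact test rejects at U ≤ 7 (90/12,870 = 0.0070), and the overall rate is about 3.5% at correlation 0 and 1.9% at 0.9. That is legitimate and keeps significance claims open on every outcome, but each test must then clear U ≤ 7 instead of U ≤ 13 with only 8 patients per group.

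**Conclusion.** The concern holds. The omission is plain in the documents as supplied: five unranked outcomes, one threshold and no rule for which result decides.

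If any one result counts, the chance of at least one false group difference is about 11% to 23%, or between roughly 1 in 9 and 1 in 4.4, against 4.99% for a single named test. This rests on one continuous variable per instrument, two-sided tests and assumed correlations from 0.9 down to 0. If the diary and urodynamics give three variables each, the range is about 14% to 37%. The omission is certain; the exact size of the error depends on correlations and a test count that the documents do not give.

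The gap does not stop the trial from running, but it weakens any positive result and should be closed.

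**What to change.** Before any between-group outcome comparison is run:

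1. Name one primary outcome and time point, chosen by the sponsor (for example, the OAB-V8 total after session 10).
2. State whether the after-treatment score or the change from baseline is compared.
3. Test it with the planned Mann-Whitney U test at two-sided 0.05.
4. Replace the SAP's threshold sentence with: *Only the primary between-group comparison will be described as statistically significant at p < 0.05. All other outcomes and all correlations are exploratory and will be reported as estimates with confidence intervals, without claims of significance.*
5. Name the interval methods, for example a Hodges–Lehmann shift with its matching interval for continuous outcomes.

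The planned test and sample size do not change, and the chance of a false significance claim returns to 4.99%. Keeping significance claims on the other four outcomes through a separate Holm procedure, alongside the primary test at 0.05, would not achieve this: the overall rate would be 8.9% at correlation 0 and 5.7% at 0.9.

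The cost is Protocol and SAP wording plus an interval for each reported estimate. The sponsor must commit to one outcome in advance and can no longer call secondary results statistically significant.
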